We will utilize published models for predicting mortality in patients with AAH to stratify patients

based on severity. Although previous studies of treatment for severe AAH utilized 30-day mortality as an endpoint, 6-month mortality is a more relevant outcome, in part because most transplantation programs require 6 months of abstinence before active listing. Furthermore, the number of deaths between 6 and 12 months in abstinent patients is low compared to the number in the first 6 months. Patients will be stratified into those with Model of End-stage Liver Disease (MELD) score ≤ 20 and MELD ≥ 20 . Those stratified into the moderate group are described in a separate application. The primary difference between the Maddrey discriminant function (DF) and the MELD is that the latter includes creatinine. We propose to use the MELD score to stratify for severity but require that patients in the severe group also have a DF > 32 , to avoid including patients with chronic kidney disease, not hepatorenal syndrome.

Specific Aim 1 = Randomized controlled trial for severe acute alcoholic hepatitis: MELD ≥ 20

: Patients with severe AAH will be randomized equally into two arms. Patients with MELD 20-25, patients with MELD 26-31, and patients with MELD \geq 32 will be randomized separately into two equal arms to ensure comparable severity in the three groups. The trial will also be double-blinded by re-packaging all oral medications into capsules to ensure that each group receives an equal number of capsules each day for the entire duration of the study.

Patients will be treated with pentoxifylline 400 mg three times daily for 28 days PLUS zinc supplements for a total of 6 months (Group A) or methylprednisolone 32 mg daily for 28 days PLUS placebo capsules daily for the remaining 5 months (Group B). An injection of either anakinra (100 mg), Group A or a placebo (Group B) will be given subcutaneously each day for 14 days. Patients, investigators and physicians involved in the care of the patients will be blinded as to the treatment.

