The primary outcome will be 6-month mortality. Secondary outcomes will include 30 and 90 day mortality; changes in MELD score at 30, 90 and 180 days and changes in gut mucosal permeability measured by serum tests. Serum endotoxin levels and serum cytokine profiles (IL-1, TNF1, etc.) will also be measured in both groups at baseline, 2, 7, 30, 90 and 180 days. The attached table indicates the timing of samples performed both for research purposes and for insuring standard of care for the subjects.

Specific Aim 2 = Natural history of severe acute alcoholic hepatitis: MELD ≥ 20 :

Patients with severe AAH who decline to be randomized but consent to prospective data collection and minimal risk non-invasive studies (blood drawing and urine collection). We will also look to enroll subjects with alcoholic hepatitis/alcoholic liver disease who are not eligible for the Drug Trial but who are willing to provide specimens and data, valuable information regarding the natural history of alcoholic hepatitis and the aims noted above. Specimens including blood, urine, stool, and liver tissue if a liver biopsy is done as part of subject's standard treatment, will be collected from subjects participating in this sub study. This will be a one-time collection of specimens to follow the procedure of the Study Day 0 for all enrolling participants.

Specific Aim 3 = Subjects will be asked for a DNA blood draw during the first day of the study.

All human subjects will be patients with a clinical presentation consistent with acute alcoholic hepatitis (AAH). The trial is designed to test the hypothesis that AAH results from inflammation triggered by gut derived endotoxins and other bacterial products as a consequence of increased permeability of the gut mucosa. Patients with AAH will be stratified by disease severity as determined by the Model for End-Stage Liver Disease (MELD) score and enrolled in one of two randomized controlled trials.

Subject population: The total subject population will be 260 patients with alcoholic hepatitis, 130 in each disease severity group (moderate disease is defined as MELD ≤ 20 and severe disease as MELD 20-25, MELD 26-31, and MELD > 32). The age range will be 21 – 70 years old. The health status of the population will be that of a group with significant acute clinical presentation from alcoholic liver disease.

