Sampling plan: The sample size was calculated based on the analysis of patients with alcoholic liver disease in the (SRTR) database, accounting for drop-out, lost-to-follow-up and non-evaluable results and including a factor for possible non-representativeness of the original database. In addition, preliminary data for 114 patients meeting criteria were used in the calculations and stratification decisions.

4. Criteria for Inclusion of Subjects:

- a. Ability to provide informed consent by subject or appropriate family member
- b. Age between 21-70 years
- c. Recent alcohol consumption > 50 g/d for > 6 months, continuing within two months before enrollment
- d. At least 2 of the following symptoms or signs of acute alcoholic hepatitis: Anorexia, nausea, RUQ pain, jaundice, leukocytes, hepatomegaly, AND
- e. Elevation of AST ≥ 50 U/L, but < 500 U/L at the time of admission or within 3 days of baseline visit; AST $>$ ALT and ALT < 200 U/L; total bilirubin > 3 mg/dL ANDf. Liver biopsy showing alcoholic hepatitis (steatohepatitis) OR ultrasound of liver showing increased echogenicity OR CT scan showing decreased attenuation of liver compared to spleen or MRI showing fatty liver (decreased signaling intensity on T1 weighted images). If the liver biopsy (done within 60 days of inclusion) confirms diagnosis of AAH then inclusion e will be waived.
- g. Model for End-Stage Liver Disease (MELD) ≥ 20 and Maddrey ≥ 32
- h. Willingness to utilize two reliable forms of contraception (both males and females of childbearing potential) from screening through the first six weeks of the study

5. Criteria for Exclusion of Subjects:

- a. Hypotension with BP $< 80/50$ after volume repletion
- b. Pregnancy; incarceration; inability to provide consent or lack of appropriate family member

- c. Signs of uncontrolled systemic infection: Fever $> 38^{\circ}\text{C}$ and positive blood or ascites cultures on appropriate antibiotic therapy for ≥ 3 days within 3 days of inclusion
- d. Acute gastrointestinal bleeding requiring > 2 units of blood transfusion within the previous 4 days
- e. Undue risk from immunosuppression: Positive HBsAg; a positive skin PPD skin test, a positive quantiferon, or history of treatment for tuberculosis; history of any malignancy except skin cancer but including hepatocellular carcinoma; known HIV infection

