- f. Treatment with corticosteroids or other immunosuppressive medications including specific anti-TNF therapy (not including pentoxifylline), calcineurin inhibitors for > 3 days within 3 days of inclusion.
- g. Evidence of acute pancreatitis: CT evidence or amylase or lipase $> 5 \times \text{ULN}$
- h. Serious cardiac, respiratory or neurologic disease or evidence of autoimmune hepatitis, primary biliary cirrhosis, primary sclerosing cholangitis, Wilson disease, hemochromatosis, secondary iron overload due to chronic hemolysis, alpha-1-antitrypsin deficiency
- i. Acute or chronic kidney injury with serum creatinine $> 3.0 \text{ mg/dl}$.

6. Study Procedures:

Aim 1

Patients will be screened, stratified as moderate or severe acute alcoholic hepatitis and randomized to one of two arms for the clinical trial. Randomization will be in blocks of 6 using a sealed, opaque envelope. The study procedures are tabulated and divided into standard of care ("Standard") and research-specific ("Research") studies. Between days 2 and 7, between days 8 and 27, at 2 months, 4 months and 5 months follow-up, clinically indicated standard studies will be obtained. Study procedures are described in the table.

Study Procedures by Study Day:

A summary of evaluations is located in the schedule of events table provided at the end of this section. The procedures and evaluations are outlined below.

Screening:

Complete screening for eligibility will occur once the informed consent has been obtained as described above. Patients will be evaluated on the basis of clinical and laboratory data during pre-screening and stratified into moderate or severe alcoholic hepatitis. Patients will be evaluated for entry into the study according to the stated inclusion and exclusion criteria. Individuals who are identified during screening as not eligible for the study need not complete all screening procedures but will be provided the option to enroll in the natural history study. The reason for ineligible status will be documented on the Screen Failure Log.

The following procedures will be obtained or performed to evaluate each patient's general health and qualifications for participation in the study:

- Signed, written informed consent
- Demographic information including gender, date of birth, race and ethnicity.
- Medication history over the past 30 days, including prescription and non-prescription over-the-counter medications, herbal medications, vitamins and minerals.

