The potential benefits to every subject participating in the clinical trial are related to receiving optimal patient-centered care for their condition. This includes ensuring the mobilization of available resources for rehabilitation programs and the education of all involved patients and their families on the possible consequences of alcohol consumption, particularly in high risk sub- populations. While ideally occurring in the care of all patients with alcoholic hepatitis, the study team will provide patients with the personal healthcare navigation assistance that is not available to every individual.

There may be immediate additional benefits to those in the active study arms if the outcomes are favorable. If the outcomes are favorable, all patients with severe alcoholic hepatitis may benefit from extrapolation of the findings. If the outcomes are negative, other subjects will be protected from the risks of treatment that has no additional benefit to convey.

There is a potential societal benefit in the general outcomes of the clinical trial with respect to alcohol consumption, alcoholism and alcoholic liver disease. In addition, the potential financial benefits of a successful program are substantial.

13. Biostatistics:

Sample size for study of patients with moderate acute alcoholic hepatitis

To compare change from baseline in the two groups of moderate AAH patients, we find that a two-sided two sample t-test of change in MELD score from baseline (mean=17.0) to 30 days with an overall sample size of 108 patients (54 in each treatment group) achieves 80% power with an alpha level of 0.05 to detect a difference in mean change of MELD score of 5.0 in the control group compared to a mean change of 8.0 in the intervention (probiotic) group with a common estimated group MELD score standard deviation of 5.559.

Adjusting for a total of 20% withdrawal, lost to follow-up or non-evaluable, we have $n^* = 108 / (1 - 0.20) = 108 / 0.80 = 136$ patients total or 68 patients in each treatment group. We expect that, in a multivariate model, we will have the power to detect smaller treatment group differences due to the partition of the variance among the predictors.

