Statistical analysis plan: Our primary analysis of change in MELD score from baseline to 30 days will be an unadjusted comparison of change (Day 30 – Baseline) using a standard two- group t-test at a two-sided alpha level of 0.05 with appropriate adjustment for unequal variances. We will also conduct secondary analyses to further investigate factors that influence the change as well as adjust for any imbalances in patient characteristics and covariates between treatment groups. Our initial model will be an Analysis of Covariance (ANCOVA) model with change in MELD score as the outcome and with treatment group (0=control, 1=probiotic) and baseline MELD score as predictors. Additional models will include patient characteristics such as age, gender, time since diagnosis as well as other covariates such as ALT, AST, and other laboratory measures at baseline. Finally, as it is likely that MELD score can be calculated throughout the duration of the study, we will use mixed models to analyze the longitudinal MELD score data. Mixed (random effects) models are used to adjust for the inherent correlation among the laboratory (and, thus, MELD score) measures on the same patient. We will consider treatment as a fixed effect, but most other factors as random effects. The model will also include a time metric, so that, rather than the change from baseline, we can use the coefficients of the times as estimates of the change from baseline (time=0), adjusted for the other factors in the model. So, for example, if MELD score is calculated at Days 0, 7, 14, 21, and 30, the model might look like: $MELDt = \beta_0 + \beta_1*tx + \beta_2*gender + \beta_3*age + \beta_4*Day7 + \beta_5*Day14 + \beta_6*Day21 + \beta_7*Day30$ where $MELDt$ = MELD score at time t ($t=0, 7, 14, 21, 30$), $\beta_0 \dots \beta_7$ = regression coefficients, tx = treatment (0=control, 1=probiotic), $gender$ = patient's gender (0=female, 1=male), age =patient's age at last birthday, $Day7$ = MELD score at Day 7 (0=No, 1=Yes), ..., $Day30$ = MELD score at Day 30 (0=No, 1=Yes). This implies that the baseline MELD score is represented by $Day7=Day14=Day21=Day30=0$. Interpreting this model, which makes maximum use of all available MELD scores, the coefficient β_4 is the estimate of the change in MELD score from baseline to Day 7, β_5 is the estimate of the change in MELD score from baseline to Day 14, etc. By combining all of the information into a single model, we can adjust the MELD score changes for other factors as well as test for a difference in the slopes of the changes between the two treatment groups. The model can, of course, be extended beyond 30 days if measures are available. The fit of the model will be assessed primarily through the likelihood ratio test of the fitted model to the intercept only model. All coefficients will be tested for significance at a critical level of $p=0.05$.

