Statistical analysis plan: Our primary analysis of this outcome will be the unadjusted log-rank test of the Kaplan-Meier survival estimates for the two treatment groups at a two-sided alpha level of 0.05 with survival censored at 6 months. Secondary analysis will use a Cox proportional hazards regression model (with survival censored at 6 months) to adjust the treatment difference in survival for patient characteristics (e.g., age, gender, time since diagnosis) and other covariates (e.g., ALT, AST, other lab measures). Predictors will be added to the model using reference cell coding, as with the mixed models above. The Cox model generates estimates of the hazard ratio for each factor compared to the reference level; e.g., for male patients vs. female patients, assuming gender = 1 for male and 0 for females, a hazard ratio of 1.25 indicates that males have a 25% higher probability of death overall by 6 months compared to females. We can also add time-dependent covariates to the model, such as ALT levels at 2 and 4 months, to estimate their predictive value for mortality. To assess the fit of the model, we will use Nagelkerke's R² constructed from the ratio of the likelihoods for the fitted model to the intercept only model. As further secondary analysis, we can eliminate the survival censoring

at 6 months and test the overall survival throughout the duration of follow-up.

General analysis plan for experiments with fold change as the outcome: Initial analyses will be descriptive in nature, allowing for investigation of appropriate normalization approaches. Initial comparative analyses of fold-change between treatment groups (or between other groups of interest) will be through a standard two-group t-test at the p=0.05 level with appropriate adjustment for unequal variances. If the fold change data are longitudinal in nature, we will use mixed (random effects) models to estimate the change in fold-change over time. In these models, fold-change at each time point will be the outcome with treatment (or other group indicator) and time as predictors. Additional patient characteristics can be added to the model to create adjusted estimates of treatment (or other group) differences. Mixed models can adjust for the correlation due to measures within patients and due to repeated microarrays at each time point.

References

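### Severe trial: randomisation is stratified by MELD band, but the primary log-rank test ignores the bands; stratifying the test would gain power at no cost in patients

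*Combined protocol and SAP*

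**What the plan says.** **Randomisation.** Section 3, Specific Aim 1, takes three MELD bands (20-25, 26-31, and 32 or above) and says that patients in each band "will be randomized separately into two equal arms to ensure comparable severity in the three groups". Section 6, Aim 1, adds: "Randomization will be in blocks of 6 using a sealed, opaque envelope". That sentence does not mention the bands. Under Subject population in Section 3 the bands appear again, as "severe disease as MELD 20-25, MELD 26-31, and MELD > 32", which leaves a MELD of exactly 32 in no band.

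**Primary analysis.** Section 13, severe trial: "Our primary analysis of this outcome will be the unadjusted log-rank test of the Kaplan-Meier survival estimates for the two treatment groups". The test is two-sided at 0.05 with survival censored at 6 months.

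**Secondary analysis.** The Cox model's covariates are given only as examples: age, gender, time since diagnosis, ALT, AST and other laboratory measures. Neither MELD nor MELD band is named. Nothing elsewhere calls for a stratified log-rank test or a stratified Cox model in the severe trial.

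**Moderate trial, for comparison.** The primary analysis there is also unadjusted. Its secondary ANCOVA does name the severity score: "and with treatment group (0=control, 1=probiotic) and baseline MELD score as predictors".

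**The concern.** Blocked randomisation within bands forces the arms to be nearly equal in band composition. If the bands predict death, the log-rank numerator then varies less from trial to trial than it would under simple randomisation. The unstratified variance formula does not credit this. The test statistic is therefore too small on average, and the test rejects a true null less often than 5%. Pooling bands with different death rates also pulls the overall hazard ratio towards 1 relative to the within-band ratio. A stratified test compares arms within band and avoids both losses.

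What is at stake is power. With only about 33 to 35 deaths expected, a prognostic factor that is already collected and already balanced should be used. The validity of the result is not at stake.

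**Working it through.** **Inputs from the plan (Section 13, severe trial, and Sections 3 and 6).** 130 patients, 1:1; two-sided alpha 0.05; 6-month survival 0.64 (control) and 0.82 (treatment); drop-out 10% per arm over 6 months; censoring at 6 months; three bands; blocks of 6, taken here to be within band.

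**Check of the plan's figures.** HR = ln(0.82)/ln(0.64) = 0.1985/0.4463 = 0.4447, as stated. With drop-out hazard g = -ln(0.9) = 0.1054 per 6 months, the probability of an observed death is λ/(λ+g) × (1 - e^-(λ+g)):
- Control: 0.4463/0.5517 × (1 - 0.64 × 0.9) = 0.343.
- Treatment: 0.1985/0.3038 × (1 - 0.82 × 0.9) = 0.171.
- Expected deaths: 65 × 0.343 + 65 × 0.171 = 33.4.

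The Schoenfeld formula gives power Φ(√33.4/2 × |ln 0.4447| - 1.96) = Φ(0.38), about 65%. The simulations below start at 62-63%. The gap from the planned 80% is a separate sample-size matter and adds no weight here.

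**Assumptions (not in the documents).** The step HR, r, is the hazard ratio between adjacent bands, varied from 1.0 to 3.0. The band mix is 50/35/15%, 40/40/20% or equal thirds. Survival is exponential.

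**Setting the band hazards.** With time in units of 6 months, choose a so that Σ wᵢ exp(-a·rⁱ⁻¹) = 0.64. Example, 50/35/15% and r = 2: a = 0.2666 gives band survival 0.766, 0.587 and 0.344, and 0.5 × 0.766 + 0.35 × 0.587 + 0.15 × 0.344 = 0.640. Two readings of the planned effect were used:
- *Reading A*: overall treatment survival stays at 0.82. In the example a within-band HR of 0.427 gives 0.5 × 0.892 + 0.35 × 0.796 + 0.15 × 0.634 = 0.820.
- *Reading B*: the within-band HR is 0.4447, so overall treatment survival becomes 0.5 × 0.888 + 0.35 × 0.789 + 0.15 × 0.622 = 0.814.

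**Tests compared.** Unstratified: Z = U/√V from pooled risk sets. Stratified: Z = Σ U_b / √(Σ V_b), with U_b and V_b computed within band b. Each power cell used 12,000 simulated trials (standard error about 0.4 points).

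| Step HR | Control 6-month mortality by band, 50/35/15% | Same, equal thirds | A: unstratified vs stratified power | A: gain (points) | B: unstratified power | B: gain (points) |
|---|---|---|---|---|---|---|
| 1.0 | 36/36/36% | 36/36/36% | 62-63% vs 62-63% | 0 | as A | 0 |
| 1.5 | 28/39/53% | 25/35/48% | 63% vs 63-64% | about 1 | 62-63% | 1 |
| 2.0 | 23/41/66% | 19/34/56% | 63% vs 66-67% | 3 | 60-61% | 3 |
| 2.5 | 20/42/75% | 14/32/62% | 64-65% vs 69-71% | 5-6 | 57-58% | 6 |
| 3.0 | 17/43/82% | 11/30/66% | 65-66% vs 72-73% | 8 | 54-56% | 8-10 |

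Under B the stratified power stays at 62-65%. At step HR 1.0 the unrounded difference was -0.3 to -0.1 points, within simulation error of zero.

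**Null rejection (100,000 trials per cell).**

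| Mix | Step HR | Unstratified | Stratified |
|---|---|---|---|
| 50/35/15% | 2.0 | 4.03% | 5.10% |
| 50/35/15% | 3.0 | 2.67% | 5.06% |
| Equal thirds | 2.0 | 3.92% | 5.00% |
| Equal thirds | 3.0 | 2.72% | 5.05% |

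**Other mixes.** With a small top band (65/30/5% or 75/20/5%, Reading A) the gain falls to 0.2-0.3 points at step HR 1.5, about 1.5-1.9 at 2.0 and 6-6.5 at 3.0.

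**In patients.** For a 50/33/17% mix at step HR 2.0, a 6,000-trial run gave 64.1% vs 67.4%. The equivalent sample-size ratio is ((0.451 + 1.96)/(0.361 + 1.96))² = 1.08, or about 8% more patients.

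**The case against.** The planned test is legitimate and matches the sample-size method, and the moderate trial follows the same pattern of a simple primary analysis and adjusted secondary ones. All of that stands, so this is a choice between two acceptable analyses.

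The evidence that the bands predict death is indirect. The sentence "We will utilize published models for predicting mortality in patients with AAH to stratify patients" leads into the split between moderate and severe disease, not into the three bands, whose stated purpose is comparable severity. This also stands: prognostic value within the severe group is plausible and is presumably why the bands exist, but the protocol does not quantify it. The creatinine exclusion could also make the top band small, which shrinks the gain. The conclusion survives because the downside is negligible even when the bands carry no information.

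For the moderate trial the plan says of adjusted modelling: "we will have the power to detect smaller treatment group differences due to the partition of the variance among the predictors". That concerns a continuous outcome and does not carry over directly to a log-rank test. It is not relied on for the size of the gain.

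MELD could enter the Cox model as a laboratory measure. True, but the plan does not commit to it.

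Finally, stratifying changes the reported effect to a within-band hazard ratio, and replacing a primary test is a formal amendment. Both are correct and belong in the fix.

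**Conclusion.** The point holds as an efficiency improvement. The design balances the arms on MELD band, and neither the primary test nor any committed secondary model uses that balance. For step HRs up to 2.0 the gain from stratifying is about 0 to 3 points of power at 130 patients, and the two readings of the planned HR give similar gaps. Gains of 5 to 10 points need step HRs of 2.5 to 3.0 at the three main mixes, with control mortality of roughly 11-20% in the lowest band and 62-82% in the highest. No scenario reached 80% power, so stratification does not cure the sample-size shortfall. The direction is secure. The size rests on assumed band mortality, assumed mixes and exponential survival.

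**What to change.** In Section 13 (severe trial), replace the primary-analysis sentence with wording such as:

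> The primary analysis is a two-sided log-rank test at alpha 0.05, stratified by the MELD band used at randomisation, with survival censored at 6 months. The hazard ratio is estimated from a Cox model stratified by the same bands. The unstratified log-rank test is reported as a sensitivity analysis.

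Then:
- Define the three bands once, matching the randomisation lists, and use that definition in both places in Section 3. State in Section 6 that the blocks of 6 are within band.
- Say that the reported hazard ratio is a within-band ratio and so is not the same quantity as the 0.4447 derived from overall survival.
- Make the change before anyone who chooses the analysis has seen outcomes by arm. Section 10 has the trial biostatistician prepare periodic safety reports, so the amendment should record who had seen what.
- The Sampling plan in Section 3 says "preliminary data for 114 patients meeting criteria were used in the calculations and stratification decisions". If those patients have 6-month outcomes, tabulate mortality by band to see which row of the table applies.

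The cost is a short protocol amendment with its approval. Baseline MELD is already needed for eligibility and randomisation, so no extra patients or data are required.

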
Sample size for study of patients with severe acute alcoholic hepatitis

Using the Lakatos approach(19) to estimating the sample size for a log-rank test, we find that a two-sided logrank test with an overall sample size of 130 patients (65 patients each of the control and treatment groups) achieves 80.0% power at a 0.05 significance level to detect a hazard ratio of 0.4447 when the proportion surviving at 6 months in the control group is 0.64 and 0.82 in the treatment group. The total study duration is 2.5 years of which subject accrual (entry) occurs in the first 2 years. We assume that the accrual pattern is uniform throughout the accrual period and that the proportion drop-out in each group is 0.10 during the 6 months with no treatment cross-overs. As a sensitivity analysis of these estimates, we used the Lachin- Foulkes approach⁽²⁰⁾, a slightly less flexible approach and, with the same assumptions as above, we estimate 53 patients in each group, reasonably close to the Lakatos estimates. Thus, to be conservative in our estimates, we will set our

sample size as 130 patients total or 65 patients in each treatment group. PASS II (NCSS, Kaysville, Utah) was used for all sample size calculations⁽²¹⁾.

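### The secondary Cox analysis explains a hazard ratio as a ratio of 6-month death probabilities, which modestly overstates relative effects for fixed covariates under proportional hazards

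*Combined protocol and SAP*

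**What the plan says.** The passage is in section 13 (Biostatistics), in the statistical analysis plan for severe acute alcoholic hepatitis. The primary analysis there is an unadjusted log-rank comparison of the Kaplan-Meier curves, censored at 6 months. A Cox model with the same censoring is secondary and adjusts the treatment difference for patient characteristics and laboratory values. The plan says that the model yields a hazard ratio for each factor against its reference level, and illustrates this with gender: "a hazard ratio of 1.25 indicates that males have a 25% higher probability of death overall by 6 months compared to females".

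The sample-size paragraph for the same study, also in section 13, relates hazard ratios to survival in a different way. Its stated target is this: "detect a hazard ratio of 0.4447 when the proportion surviving at 6 months in the control group is 0.64 and 0.82". The second survival figure is for the experimental arm.

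No other part of the document qualifies or corrects the gender example.

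**The concern.** The example names a cumulative quantity at a fixed time, the probability of having died by 6 months. A Cox hazard ratio is a ratio of instantaneous rates. The two nearly coincide when deaths are rare, but this trial is designed around 18% and 36% mortality at 6 months.

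The primary outcome is 6-month mortality, so the example misreads the hazard ratio on the scale that readers will care about most. The Cox hazard ratio is also the only effect measure that this part of the plan names, and the gender example is the only guidance on how to read it. An analyst who followed it when writing up the adjusted results would quote percentage changes in 6-month mortality that are too large. What is at stake is the reporting of secondary effect sizes, not the validity of any test.

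**Working it through.** **Inputs**
- HR 1.25, read as 25% more deaths by 6 months: section 13, analysis plan for severe disease.
- Design HR 0.4447, with 6-month survival of 0.64 (control) and 0.82 (treatment), that is, 36% and 18% deaths: section 13, sample size for severe disease.
- Background 6-month mortality of 30% to 50%: section 2.
- Mortality in females, the reference group of the example: not given. I assume 18%, 27% and 36% (the two design rates and their mean) and also show the background range.

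**Step 1. Reproduce the plan's figure.** Under proportional hazards, S1(t) = S0(t)^HR, so HR = ln S1 / ln S0.

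ln(0.82) / ln(0.64) = (−0.1985) / (−0.4463) = 0.4447. This matches the plan.

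**Step 2. Compare with the risk ratio in the same paragraph.** 0.18 / 0.36 = 0.50. The HR of 0.4447 and the risk ratio of 0.50 describe the same pair of survival figures, so they are different quantities.

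**Step 3. Apply the example's reading to the design HR.** 1 − 0.4447 = 0.555, a 55.5% reduction, or 0.36 × 0.4447 = 16.0% deaths in the treatment arm. The design figures are a 50% reduction and 18% deaths.

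**Step 4. Convert HR 1.25 properly.** With reference mortality p, the comparison group's mortality is 1 − (1 − p)^1.25, and the risk ratio is that value divided by p.

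| Assumed reference mortality p | Mortality at HR 1.25 | Risk ratio | Mortality if HR is read as a risk ratio (1.25 × p) |
|---|---|---|---|
| 18% | 22.0% | 1.220 | 22.5% |
| 27% | 32.5% | 1.205 | 33.75% |
| 36% | 42.8% | 1.188 | 45.0% |
| 30% (background, low) | 36.0% | 1.199 | 37.5% |
| 50% (background, high) | 58.0% | 1.159 | 62.5% |

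**Step 5. Direction.** For HR above 1, 1 − (1 − p)^HR is less than HR × p. For HR below 1 it is greater. The risk ratio is therefore always closer to 1 than the HR, and reading one as the other exaggerates in both directions.

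**Step 6. The reverse check.** The HR needed for a true 25% increase in 6-month deaths is ln(1 − 1.25p) / ln(1 − p). This is ln(0.775)/ln(0.82) = 1.28 at p = 18%, and ln(0.55)/ln(0.64) = 1.34 at p = 36%.

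**The case against.** The case for leaving this alone has real substance.

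- **It is an illustration.** The sentence is a parenthetical example about gender in a secondary analysis. Nowhere does the plan say that the treatment effect will be reported as a percentage change in 6-month death probability. This stands. The lead-in does cover each factor, so carrying the reading over to treatment is a fair inference, but it remains an inference.
- **The primary result is untouched.** A reader might infer that the primary mortality comparison is biased. It is not. The log-rank test, its alpha level, the design HR and the sample size do not use the example.
- **The plan does not get its own design HR wrong.** A reader might infer a contradiction in the sample-size paragraph. That paragraph is correct and never treats the HR as a risk ratio. The 55.5% appears nowhere in the document; it results only from applying the gender example's reading to the design HR.
- **The gap is small beside sampling error.** With about 130 × 0.27 = 35 deaths (ignoring dropout), the standard error of the log HR is roughly 2/√35 = 0.34. The 95% CI around 0.4447 then runs from about 0.23 to 0.86. This is true, but sampling error does not excuse a systematic misreading in one direction.
- **Not every effect converts this way.** The plan also allows time-dependent covariates, such as ALT at 2 and 4 months. The simple power relation does not apply to those, so a claim that every effect is overstated goes too far.

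**Conclusion.** The example is wrong as written and should be corrected, but it is a limited error of interpretation. For fixed covariates under proportional hazards, it overstates the relative change in 6-month mortality. At an assumed reference mortality of 18% to 36%, an HR of 1.25 corresponds to about 22% to 19% more deaths by 6 months, an overstatement of about 3 to 6 percentage points in the quoted relative effect. Over the background range of 30% to 50%, the true increase is 19.9% to 15.9%. For an effect of the design size, the misreading would be 55.5% against 50%.

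The direction follows from proportional hazards alone. The size depends on the reference mortality, which is assumed because the document does not give it for females. The consequence is confined to how secondary Cox results might be described.

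**What to change.** Reword the example along these lines: *for males against females, HR = 1.25 means a 25% higher hazard (rate) of death during the 6 months.* That alone cures the error.

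Add that any statement about the probability of death by 6 months will come from the Kaplan-Meier estimates by arm, reported with their difference and 95% CI. The curves are already planned, so no new data or model is needed, although the plan does not yet commit to reporting the difference and its interval.

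The cost is one sentence in the analysis plan and one line in a results table. Percentage effects quoted for 6-month mortality become slightly smaller.
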